## 11 Study Calendar

**Table 2. Study Calendar**

	Eligibility screening	Cycle 1, Day (-28) e	Pre-op evaluation (1 to 3 days before surgery)		off Apalutamide follow-up visit in 4 -8 weeks after RP h
Leuprolide IM injection + Apalutamide distribution		X a		Prostatectomy  (Day of surgery) k	
Tissue Core Biopsy from Initial Diagnosis		X			
MRI Prostate b					
Informed consent		X			
Demographics		X			
Medical History		X	X		X
Prior and concomitant medication review c		X	X		X
Vital Signs		X	X		X
Height/Weight/BSA		X	X		X
Physical Exam		X	X		X
Performance Status		X	X		X
CBC/diff, platelets		X	X l		X
Serum chemistries d		X	X l		X
TSH l		X	X		X
PT/PTT		X	X l		
Genotyping Analysis	X e				
Evaluation of AE's		X	X	X	
PSA		X	X l		
Testosterone, DHEA, DHEA-S, Androstenedione, Direct Renin and Aldosterone/Direct Renin Ratio		X	X l		
Blood for Correlative Studies f	X			X	

a: Study agents include Apalutamide. Patients will receive these medications for the entire treatment course at Day (-28) ± 3 days up to and including the day before prostatectomy (day of surgery).

b: MRI of the prostate will be completed at the discretion of the treating Physician. Although this imaging technique is routinely done at the Cleveland clinic prior to patients undergoing RP, it will be desired but not be mandatory for study entry.

c: Refer to Section 7.3 for further details on reporting prior and concomitant medications.

d: Sodium, potassium, chloride, CO2, BUN, Creatinine, Glucose, LFT's (AST/ALT/Alkaline Phosphatase, Albumin, LDH, total bilirubin), and Calcium. Testosterone, PSA, DHEA, DHEA-S and

AD levels will be measured within 28 days of treatment initiation and at the end of C1 of therapy as above.

e: Blood will be drawn for *HSD3B1* genotyping for the research laboratory.

f: Blood draw for steroid concentration in the serum and to understand how tumors use and make hormones. This sample will be sent to [name] lab.

g: Laboratory tests and procedures must be completed on Cycle 1 Day (-28) or within 28 days prior to the start of study agents Leuprolide IM injection and Apalutamide distribution.

h: Post-operative follow up visit will ideally occur between 4 and 8 weeks after surgery. Time line may vary in order to coordinate with Urology follow up visit.

I: Allowable window for lab collection is 1-3 days prior to, or on, the day of prostatectomy.

J: Allowable window for lab collection is 1-7 days prior to prostatectomy.

K: Must be completed within 28 days  $\pm 3$  from the start of Leuprolide IM injection and Apalutamide distribution.

L: Thyroid stimulating hormone (TSH) should be evaluated throughout the study (with T3 and T4 done only if TSH is abnormal) as follows: On Cycle 1 or within 28 days before treatment initiation, at the end of Cycle 1 (approximately day 28 Pre-op evaluation), and 4-8 weeks after RP (Follow Up evaluation).

## **12 Measurement of Effect**

- 12.1 Benign and malignant tissue concentration of DHT and other androgen (testosterone (T), dehydroepiandrosterone (DHEA), androstenediol, 5 $\alpha$ -androstenedione (5 $\alpha$ -dione), androstenedione (AD), androsterone and 5 $\alpha$ -androstenediol), Direct renin and Aldosterone/Direct Renin Ratio will be measured by IHC as stated in section 10 of the protocol.
- 12.2 PSA, FKBP5, TMPRSS2, EZH2, H3K27, and UBE2C expression in benign and malignant prostate tissue after neoadjuvant leuprolide and Apalutamide will be also analyzed by IHC and qPCR as noted in section 10 of the protocol.
- 12.3 Toxicity will be evaluated using standard CTC guidelines as per section 9 of the protocol. All patients enrolled on study will be evaluable for toxicity from the time of their first treatment with leuprolide and Apalutamide. Surgical safety data will be captured following standardized surgical templates routinely used in the GU clinic.
- 12.4 Although clinical endpoints are not the aim of this biologic study, results of the surgical pathology and PSA changes pre-treatment, during treatment and after surgery will be collected.

## **13 Records to Be Kept/ Regulatory Considerations**

Adverse event lists, guidelines, and instructions for AE reporting can be found in Section 9. Adverse Events: List and Reporting Requirements).

### **13.1 Data Reporting**

The Forte EDC™ and OnCore™ databases will be utilized, as required by the Case Comprehensive Cancer Center and Cleveland Clinic, to provide data collection for both accrual entry and trial data management. Forte EDC and OnCore™ are Clinical Trials Management Systems housed on secure servers. Access to data through Forte EDC and OnCore™ is restricted by user accounts and assigned roles. Once logged into the Forte EDC or OnCore™ system with a user ID and password, Forte EDC™ and OnCore™ define roles for each user which limits access to appropriate data. User information and password can be obtained by contacting the OnCore™ Administrator at [contact] for OnCore™ access, and [contact] for Forte EDC™ access.

Forte EDC™ is designed with the capability for study setup, activation, tracking, reporting, data monitoring and review, and eligibility verification. When properly utilized, Forte EDC™ is 21 CFR 11 compliant. This study will utilize electronic Case Report Form completion in the Forte EDC™ database. A calendar of events and required forms are available in Forte EDC™.

## **13.2 Regulatory Considerations**

The study will be conducted in compliance with ICH guidelines and with all applicable federal (including 21 CFR parts 56 & 50), state or local laws.

### **13.2.1 Written informed consent**

Provision of written informed consent must be obtained prior to any study-related procedures. The Principal Investigator will ensure that the subject is given full and adequate oral and written information about the nature, purpose, possible risks and benefits of the study as well as the subject's financial responsibility. Subjects must also be notified that they are free to discontinue from the study at any time. The subject should be given the opportunity to ask questions and allowed time to consider the information provided. The original, signed written Informed Consent Form must be kept with the Research Chart in conformance with the institution's standard operating procedures. A copy of the signed written Informed Consent Form must be given to the subject.

### **13.2.2 Subject data protection**

In accordance with the Health Information Portability and Accountability Act (HIPAA), a subject must sign an authorization to release medical information to the sponsor and/or allow the sponsor, a regulatory authority, or Institutional Review Board access to subject's medical information that includes all hospital records relevant to the study, including subjects' medical history.

### **13.2.3 Retention of records**

The Principal Investigator of The Case Comprehensive Cancer Center supervises the retention of all documentation of adverse events, case report forms, source documents, records of study drug receipt and dispensation, and all IRB correspondence for as long as needed to comply with national and international regulations and the institution in which the study will be conducted, or for the period specified by the sponsor, whichever is longer. No records will be destroyed until the Principal Investigator confirms destruction is permitted.

#### 13.2.4 Audits and inspections

Authorized representatives of the Cleveland Clinic's clinical trials office, a regulatory authority, an Independent Ethics Committee (IEC), a designee from the Cleveland Clinic's Institutional Review Board (IRB), or a Janssen Scientific Affairs, LLC representative may visit the Center to perform audits or inspections, including source data verification. The purpose of an audit or inspection is to systematically and independently examine all study-related activities and documents to determine whether these activities were conducted, and data were recorded, analyzed, and accurately reported according to the protocol, Good Clinical Practice (GCP), guidelines of the International Conference on Harmonization (ICH), and any applicable regulatory requirements.

#### 13.2.5 Data safety and monitoring plans

This protocol will adhere to the policies of the Case Comprehensive Cancer Center Data and Safety Monitoring Plan in accordance with NCI regulations.

#### 13.2.6 Patient's financial responsibilities during the study

13.2.6.1 There will be no cost for the Apalutamide or any of the correlative histologic and/or molecular studies. Leuprolide is considered standard of care in men with prostate cancer thus it will be billed to patient's insurance.

13.2.6.2 Charges incurred to pre-surgical evaluation, such as monitoring complete blood counts, comprehensive metabolic panel, and other necessary tests per surgical protocols will be charged to the patient's insurance company in standard fashion.

13.2.6.3 Charges incurred to monitor the safety and efficacy of this treatment, such as monitoring complete blood counts, comprehensive metabolic panel, baseline testosterone level and PSA, which are not indicated per patient's standard treatment plan, will be paid by the study grant.

## 14 Biostatistical Considerations

All subjects will be receiving Apalutamide starting day (-28)  $\pm$  3 days from the scheduled RP date and will be genotyped for *HSD3B1* before enrollment in the study as a part of the screening. We expect a higher concentration of DHT in patients with homozygous *HSD3B1*(1245C) genotype as a result of flux to DHT due to 3 $\beta$ HSD1 abundance.

### 14.1 Sample Size and Accrual

In a recent report by Chang et al the prevalence of the homozygous *HSD3B1*(1245C) genotype was 10% in 40 CRPC patients. The prevalence however is to some extent race-dependent.

The prevalence of the wild type and heterozygous genotypes were approximately 2:1, and therefore the homozygous variant genotype is “rate-limiting” for accrual. The target enrollment is 12 patients who have the homozygous *HSD3B1*(1245C) genotype, 15 patients who are heterozygous, and 30 wild-type patients. Because of the low prevalence of homozygous *HSD3B1* (1245C), enrollment in each cohort will proceed until its target is reached. A subject who either prematurely discontinues from the study before completing 28 days of the treatment, prior to surgery, or for whom we are unable to obtain a tissue sample from, may be replaced in order to achieve target enrollment in each cohort. All safety and efficacy data from all accrued patients independent of the availability of post-treatment tumor material will be collected and analyzed.

Overall, based on the prevalence of the homozygous variant genotype, we predict that we may need to screen up to 120 patients to reach our accrual objective. Due to logistical restrictions, an accrual goal of 80 male patients may be needed in order to capture all objectives for a sample size of 57 patients. Accrual is expected to be approximately 2 years in the three cohorts.

With 57 patients there will be statistical power >80% to detect a 4-fold trend in the primary endpoint, DHT concentrations in the resected prostate tissue, as well as similar trends in other androgens and molecular markers. The calculation is based on a 2-sided test with 5% type I error; a codominance model where there is a 4-fold difference in hormone concentration between the wild-type and homozygous variant genotypes and a concentration approximately mid-way between the two for the heterozygous genotype; and that variability in this concentration could be as much as 125% of the mean hormone tissue concentration for each genotype. Note that 125% of the mean is a conservative estimate of variability. If it turns out in fact to be lower – e.g. similar to the 75% seen in a recent study in which patients were treated with 6 months leuprolide prior to RP, there will be >95% power to detect a 4-fold range, >90% to detect a 3-fold range, and 75% to detect a 2-fold range.

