	
androsterone and 5<math>\alpha</math>-androstenediol) concentration in benign prostate tissue after neo-adjuvant leuprolide and Apalutamide based on genotype status
 
2. Other androgens (DHT, T, DHEA, androstenediol, 5<math>\alpha</math>-dione, AD, androsterone and 5<math>\alpha</math>-androstenediol) concentration in malignant prostate tissue after neo-adjuvant leuprolide and Apalutamide based on genotype status.
 
3. PSA, FKBP5, TMPRSS2, EZH2, H3K27, and UBE2C expression (via IHC and qPCR) in benign and malignant prostate tissue after neoadjuvant leuprolide and Apalutamide based on genotype status.

Sample Size	
Based on the known frequency of the genotypes in question, approximately 120 male patients will be genotyped prior to enrollment on study. The sample size required to carry-out the objectives of the study will be 57 male patients. Due to logistical restrictions, an accrual goal of 80 male patients may be needed in order to capture all objectives to support this sample size. There won't be any ethnic restrictions for study entry including during the initial genotype identification state.

Disease sites/Conditions	Prostate cancer
Interventions	Leuprolide acetate, Intramuscular injection - 7.5 mg, one time dose on day (-28) $\pm$ 3
	Apalutamide, PO, 240 mg daily, starting day (-28) $\pm$ 3 up to and including the day before radical prostatectomy. Apalutamide will be initiated the same day patients receive their leuprolide acetate injection.

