## 1.5 Preclinical Data

Recently, a gain of function single-nucleotide polymorphism (SNP) in *HSD3B1*(1245C; N367T) was identified that can also occur as a somatic mutation in CRPC tumors. Germline SNP variant of *HSD3B1*(1245C, rs1047303) occurs with a reported allele frequency of 22% in general population, but appears to vary widely by ethnicity. In a group of 118 prostate cancer patients at Cleveland Clinic, the frequency of the variant *HSD3B1*(1245C) allele is 36%. 3 $\beta$ -hydroxysteroid dehydrogenase isoenzyme-1 (3 $\beta$ HSD1), encoded by *HSD3B1*, is one of the three enzymes involved in converting DHEA from the adrenal gland to DHT in prostate cancer tissue. 3 $\beta$ HSD oxidizes 3 $\beta$ -hydroxyl to 3-keto and isomerizes  $\Delta^5$  to  $\Delta^4$  in the process of converting DHEA to AD. These reactions together make this step practically irreversible by an enzyme that is required for all possible pathways that lead to the synthesis of DHT. Chang et al have shown that CRPC sometimes expresses the 367T form of the *HSD3B1*, which increases metabolic flux from DHEA via the 5 $\alpha$ -dione pathway to DHT by protein resistance to ubiquitination and degradation rather than increased catalytic activity. This mutation increases protein half-life from 2.1 to 27 hours which leads to a profound accumulation of 3 $\beta$ HSD1 with subsequent increased flux to DHT and ultimately increased AR activation and prostate cancer progression. In addition, to study the possibility of *HSD3B1* (1245C) selection in human tumors, we sequenced matching germline and tumor DNA from 40 men with CRPC. Among these patients, the germline of 25, 11, and 4 individuals was homozygous wild type *HSD3B1* (1245A), heterozygous, and homozygous variant *HSD3B1* (1245C), respectively. Three of 25 (12%) CRPC tumors with homozygous *HSD3B1* (1245A) inheritance have acquired the *HSD3B1* (1245C) allele. Also, three of 11 (27%) CRPC tumors with heterozygous inheritance, have loss of heterozygosity (LOH) of the *HSD3B1* (1245A) allele, resulting in the *HSD3B1* (1245C) allele being predominantly detectable. In contrast, none of the 11 cases with heterozygous inheritance exhibited LOH of the *HSD3B1*(1245C) allele. These data support the role of the *HSD3B1* (1245C) allele in the development of CRPC. Moreover, our review of the clinical outcomes in 118 men with prostate cancer who were treated with ADT for biochemical failure after prostatectomy shows that inheritance of *HSD3B1*(1245C) allele that enhances the DHT synthesis may predict resistance to ADT in prostate cancer. In this group of patients allelic frequency of *HSD3B1* (1245C) was 36% with homozygous wild-type, heterozygous, and homozygous variant detected in 37%, 53%, and 10% of the patients. We demonstrated that median progression free survival (PFS), distant metastasis-free survival (DMFS), and overall survival (OS) diminished as a function of the number of variant alleles inherited, showing a gene-dosage effect and stepwise decrements with 0 vs. 1 vs. 2 variant alleles in all three endpoints.

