## 2 Objectives

### 2.1 Primary Objective

To evaluate the differential effect of neo-adjuvant leuprolide and Apalutamide on dihydrotestosterone (DHT) concentration in benign prostate tissue based on *HSD3B1* genotype.

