### **4.3 Inclusion of Minorities**

Men of all races and ethnic groups, English or non-English-speaking are eligible for this trial.

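### Does the comparison of DHT between genotype cohorts need a prespecified race-adjusted analysis?

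*Combined protocol and SAP*

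**What the plan says.** The primary objective (section 2.1) is "To evaluate the differential effect of neo-adjuvant leuprolide and Apalutamide on dihydrotestosterone (DHT) concentration in benign prostate tissue based on" HSD3B1 genotype. All men receive the same regimen, so the contrast is between inherited groups. Section 14.1 sets targets of 30 wild-type, 15 heterozygous and 12 homozygous men, and "enrollment in each cohort will proceed until its target is reached". It plans no balancing by race.

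The link between race and genotype is mentioned twice. Section 14.1, discussing accrual, says "The prevalence however is to some extent race-dependent". Section 1.5 says the variant allele frequency is 22% in the general population "but appears to vary widely by ethnicity". Entry is open: "Men of all races and ethnic groups, English or non-English-speaking are eligible for this trial" (section 4.3) and "There won't be any ethnic restrictions for study entry including during the initial genotype identification state" (Protocol Summary).

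Section 14.2 compares genotypes by models that may be linear or non-linear, with two-sided tests. It names no covariates. The registration form in Appendix II records race and ethnicity separately, each with an option for unknown.

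The main power case in 14.1 is a 4-fold range where "variability in this concentration could be as much as 125% of the mean hormone tissue concentration for each genotype". If variability is nearer 75% of the mean, it also claims "75% to detect a 2-fold range".

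**The concern.** An inherited-genotype contrast is observational. If genotype frequency differs by race and all races enrol, the racial mix may differ between the three cohorts. If race also affects DHT in benign tissue by some route other than HSD3B1, an unadjusted genotype trend would mix the two effects.

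The bias can run either way. It weakens a real genotype effect if the group with fewer variant alleles has the higher DHT, and exaggerates it if that group has the lower DHT. The study wants to attribute a DHT difference to the enzyme variant, so a reader will ask whether ancestry explains it. A check named in advance answers that better than one chosen after seeing the data. Since race is already collected, adding a supporting analysis appears to cost only wording.

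**Working it through.** **1. The plan's own power figures.** Inputs from section 14.1: n = 30/15/12, two-sided 5%, heterozygote mean midway, SD a fixed percentage of each genotype mean. The test is a least-squares trend on allele count (0/1/2) on the raw scale, with normal errors and 20,000 simulations. Section 14.2 names no primary model, so the scale is an assumption.

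| Case | Stated power | Reproduced |
|---|---|---|
| 4-fold, SD 125% | >80% | 79% |
| 4-fold, SD 75% | >95% | 99% |
| 3-fold, SD 75% | >90% | 96% |
| 2-fold, SD 75% | 75% | 77% |

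The stated powers therefore correspond to an unadjusted trend test, within about two points.

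**2. How unequal could the cohorts be?** Every race input here is assumed. The smaller group is 20% of men. Its allele frequency against the rest is 10% vs 40% (wide gap; no source in the documents) or 22% vs 36% (narrow gap; both figures are in section 1.5, but they describe the general population and a series of prostate cancer patients, not races). By Hardy-Weinberg and Bayes, the smaller group's share under the wide gap is:

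- wild type: 0.2×0.9² / (0.2×0.9² + 0.8×0.6²) = 0.162/0.450 = 0.360
- homozygous: 0.2×0.1² / (0.2×0.1² + 0.8×0.4²) = 0.002/0.130 = 0.015

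The heterozygote share is 0.086. The narrow-gap shares are 0.271/0.157/0.085.

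**3. Size of the spurious effect (log scale).** Mean allele count = (15 + 24)/57 = 0.684. Sxx = 15 + 48 − 39²/57 = 36.3. The trend in the wide-gap shares is [30(−0.684)(0.360) + 15(0.316)(0.086) + 12(1.316)(0.015)]/36.3 = −0.186 per allele, or −0.371 from wild type to homozygous. A 2-fold race effect gives a ratio of 2^(−0.371) = 0.77, or its inverse 1.29. The narrow gap gives 0.88. To produce a spurious 2-fold ratio under the wide gap, race would need a 2^(1/0.371) ≈ 6.5-fold effect on DHT. For 4-fold it would need 4^(1/0.371) ≈ 42-fold.

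**4. Type I error of the unadjusted test** (no genotype effect, 20% share, 2-fold race effect):

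| | Log, wide | Log, narrow | Raw, wide | Raw, narrow |
|---|---|---|---|---|
| CV 75% | 18.5% | 8.1% | 15.4% | 7.2% |
| CV 125% | 11.7% | 6.7% | 8.0% | 5.1% |

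At CV 75% a 1.25-fold race effect gives 5.2 to 6.7%. With a 5% share and a 2-fold race effect the range is 4.7 to 6.2%.

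**5. Power of the unadjusted test** (20% share, 2-fold race effect, smaller group with the higher DHT):

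| Case | Scale | No race effect | Wide | Narrow |
|---|---|---|---|---|
| 4-fold, CV 125% | raw | 79% | 66% | 71% |
| 2-fold, CV 75% | log | 88% | 46% | 65% |
| 2-fold, CV 75% | raw | 77% | 33% | 51% |

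On the log scale the 4-fold case falls from 99% to 94% under the wide gap.

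**6. What adjustment would deliver.** The chance that none of the 12 homozygous men is in the smaller group is (1 − 0.015)^12 = 0.83 (wide) or (1 − 0.085)^12 = 0.34 (narrow). The chance of none or one is 99% or 73%. The race coefficient then rests almost wholly on wild-type and heterozygous men. On the raw scale with ordinary standard errors, the race-adjusted test's type I error ranges from 2.2 to 7.1%; robust (HC3) errors bring it to 4.6 to 5.2%. If race has no effect, raw-scale power for 2-fold at CV 75% falls from 77% to 72% (wide) or 75% (narrow) with a race term, and to 66% or 68% within the largest group.

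**The case for a change.** The best case for a change is that the protocol itself asserts half of the confounding path, in two places, and then plans nothing to examine the other half. No passage rules out a race effect on DHT. The 2-fold range is a claim that 14.1 makes, and assumed confounding can cut its power from 88% to 46%, or move a true 2-fold estimate to 1.57 or 2.63 (log scale, wide gap). The remedy needs no new data and no extra patients.

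Part of this stands. The contrast is observational, no race term is prespecified, and confounding is possible. But the largest figures need three assumptions together: the unsourced wide gap, a race effect as large as the genotype effect itself, and the lower variability that 14.1 offers only conditionally. A supporting analysis would also leave the primary test as it is, so the type I error and power above would not change. What is gained is context for interpretation, and the existing model wording and recorded race already allow that. The remedy is also less simple than it looks. Section 1.5 speaks of ethnicity rather than race, both items can be recorded as unknown, and a two-level race variable is a crude proxy for ancestry. It removes the bias in simulation partly because the same variable created it.

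**Conclusion.** No change is needed. This is an unnamed covariate in a brief analysis section of a phase II biological study, and analysts can deal with it sensibly. Tabulating race and ethnicity by genotype cohort, with unknown shown separately, is routine reporting. If the table shows imbalance, the DHT trend can also be shown descriptively with a race term or within the largest group. Whether that is worthwhile depends on the enrolled mix. With few men outside the largest group there is little to adjust for. With a strong imbalance, the adjusted estimate has almost no homozygous men in the smaller group to support it. Prespecifying a race term is therefore a trade-off rather than a clear gain.

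The conclusion rests on assumed race inputs throughout, since the documents supply none. It would be different if there were evidence that race changes benign-tissue DHT severalfold by a route other than HSD3B1 and the cohorts were known to differ strongly in racial mix. The documents show neither.

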## **5 Registration**

### **5.1 General Guidelines**

All subjects who have been consented are to be registered in the OnCore Database. Eligible patients will be entered on study centrally at the Cleveland Clinic Taussig Cancer Institute by the Study Coordinator. Following registration, patients should begin protocol treatment on day (-28)  $\pm$  3 days which is set based on the scheduled surgery date. If a patient does not receive protocol therapy as scheduled following registration, the patient's registration on the study may be canceled. For those subjects who are consented, but not enrolled, the reason for exclusion must be recorded. The Study Coordinator should be notified of cancellations as soon as possible.

A subject who either prematurely discontinues from the study before completing 28 days of the treatment, prior to surgery, or for whom we are unable to obtain a tissue sample from, may be replaced at the discretion of the PI.

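### Is the forecast of 120 men to genotype too low to fill the homozygous cohort?

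*Combined protocol and SAP*

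**What the plan says.** Section 14.1 takes a 10% prevalence of the homozygous variant from a series of 40 men and identifies that cohort as the one that governs accrual. It sets targets of 12 homozygous, 15 heterozygous and 30 wild-type men. From the prevalence it concludes: "we predict that we may need to screen up to 120 patients to reach our accrual objective". The Protocol Summary gives the same number in softer terms: "approximately 120 male patients will be genotyped prior to enrollment on study".

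Three further statements in Section 14.1 bear on what the number does:

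- Enrollment rule: "enrollment in each cohort will proceed until its target is reached".
- Men who stop before 28 days of treatment or give no tissue "may be replaced in order to achieve target enrollment in each cohort". Section 5.1 says that such men "may be replaced at the discretion of the PI".
- Accrual: "an accrual goal of 80 male patients may be needed in order to capture all objectives for a sample size of 57 patients", and "Accrual is expected to be approximately 2 years in the three cohorts".

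No section states a loss rate, a screening rate per year, or a probability that 120 will be enough.

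**The concern.** A number worded as an upper figure should carry a margin, and this one has none. It equals the mean number of men who must be genotyped to find 12 homozygotes, provided that every one found is eligible, enrolls, completes treatment and yields tissue. The plan itself expects some men to be lost and replaced, and it puts the accrual goal at 80 for a sample size of 57, yet the screening number is still exactly 12/0.10.

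Homozygous men are the scarcest group and form one end of the primary genotype contrast. If screening stopped near 120, that cohort could fall short of 12 and the contrast would lose precision. Even if screening continued, the genotyping workload and the accrual time could be underestimated.

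**Working it through.** **Inputs**

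- Homozygous prevalence 10%: 4 of 40 men (Sections 1.5 and 14.1). Section 1.5 reports a second series of 118 men with "homozygous wild-type, heterozygous, and homozygous variant detected in 37%, 53%, and 10% of the patients".
- Homozygous target: 12 (Section 14.1).
- Screening forecast: 120 (Section 14.1 and Protocol Summary).
- Loss among homozygotes: not stated. The values 0%, 10% and 20% below are assumptions.

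**1. The plan's figure.** Expected number to genotype = target / prevalence = 12 / 0.10 = 120. This reproduces the stated figure exactly, so the arithmetic is right. The number varies by chance: its standard deviation is √(12 × 0.90) / 0.10 = √10.8 / 0.10 ≈ 33.

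**2. Chance that 120 is enough.** With X the number of evaluable homozygotes among 120 men, X is binomial with n = 120 and p = 0.10 × (1 − loss). The 80% and 90% columns give the smallest n for which P(X ≥ 12) reaches that level.

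| Assumed loss | p | P(X ≥ 12) with n = 120 | Mean to genotype, 12/p | n for 80% | n for 90% |
|---|---|---|---|---|---|
| 0% | 0.10 | 0.5445 | 120 | 146 | 164 |
| 10% | 0.09 | 0.3956 | 133 | 163 | 182 |
| 20% | 0.08 | 0.2523 | 150 | 183 | 205 |

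For 90% assurance the extra genotyping would be 164 − 120 = 44 men with no loss and 205 − 120 = 85 men at 20% loss.

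**3. The other two cohorts.** With no loss, the chance that 120 men supply at least 15 heterozygotes exceeds 0.999 under either series (27.5% or 53% heterozygous). The chance of at least 30 wild-type men is at least 0.998 (62.5% or 37% wild type). The chance of meeting all three targets together is about 54% under either split, so the homozygous cohort decides the result.

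**4. Prevalence.** The 54% treats 10% as known. With no loss it becomes 25% at a prevalence of 8% and 79% at 12%. The exact 95% interval for 4 of 40 is 2.8% to 23.7%. Pooling both series, with 10% of 118 taken as 12 men, gives 16 of 158 and an interval of 5.9% to 15.9%. Across that pooled interval the chance that 120 is enough runs from 5% to 98%. Uncertainty in the prevalence therefore outweighs the chance variation in step 2.

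**5. What happens when 120 is not enough.** Under the enrollment rule in Section 14.1, genotyping continues until the homozygous cohort reaches 12. The variable quantity is the number of men genotyped; the cohort size is fixed. Genotyping is done at screening, before tissue DHT exists, so the decision to keep screening depends on genotype counts and not on the endpoint. Extending it introduces no bias and leaves the type I error as planned. The power statement depends on the three cohort sizes, the fold difference and the variability; the number screened does not enter it.

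**The case for a change.** The strongest case for a change is that a forecast is used to plan blood draws and time. One worded as a ceiling is exceeded about 46% of the time before any loss (1 − 0.5445) and about 60% of the time at 10% loss (1 − 0.3956). The plan also allows for replacement on the accrual side and not on the screening side: the Summary of Changes links the goal of 80 partly to replacing patients, yet each homozygous man replaced needs on average 1/0.10 = 10 more men genotyped. A reworded sentence would cost almost nothing.

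The probabilities stand, and so does the remark on wording. The step to a needed change does not:

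- Only the 54% follows from the plan's own inputs, and any forecast set at the mean would give something close to it. The loss rates and the 80% or 90% assurance levels are choices that the documents neither supply nor require.
- The goal of 80 cannot be turned into a loss rate for homozygotes. It is not broken down by genotype, and Section 14.1 itself attributes it to logistics.
- Section 14.1 does not derive the 2 years from 120 and gives no screening rate, so a longer accrual cannot be put in years without inventing one.
- Given the prevalence uncertainty in step 4, replacing 120 by 164 or 205 would suggest a precision that the data do not support.

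Replacement is discretionary, so a lost homozygous man might not be replaced. That would come from the replacement rule, and a larger screening forecast would not prevent it.

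**Conclusion.** The observation is correct but calls for no change. The 120 is a correctly computed average that Section 14.1 words loosely as an upper figure. The forecast verb and the approximate figure in the Protocol Summary show how to read it: on average about 120 men, before losses. At a true prevalence of 10% it suffices with probability of about 54% with no loss, or about 40% and 25% under assumed losses of 10% and 20%.

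Because each cohort enrolls to its target, a low forecast costs additional genotyping and perhaps time. It does not alter the cohort sizes, the total of 57, the power, the analysis or the conclusions. Rewording would tidy a feasibility statement and gain nothing for the trial's inference. This conclusion rests on the enrollment rule being followed as written; the documents contain no instruction to stop screening at 120.
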